5.0 Setting

5.1 *Describe the sites or locations where your research team will conduct the research. Consider each of the items listed below:*

- *Identify where your research team will identify and recruit potential subjects.*
- *Identify where the team will perform the research procedures.*
- *Describe the composition and involvement of any community advisory board(s).*
- *For research conducted in other locations, describe:*
 - *Site-specific regulations or customs affecting the research at those locations.*
 - *Local scientific and ethical review structure at those locations. Examples include work in other cultures or ethnic groups (within or outside of the U.S.) and work with churches. The HRPP will provide additional guidance for international research.*

Location of Recruitment:

Participants will be recruited from the Roanoke-Blacksburg community via flyers, word of mouth referrals, and electronic advertisements (e.g., Craigslist, Facebook). To the extent possible, we will attempt to minimize obstacles to participation. For example, travel barriers will be addressed by providing transportation or parking costs to participants, and scheduling barriers will be minimized by offering a flexible session schedule.

Location of study:

All methods and measures will be conducted using standard operating procedures at the Fralin Biomedical Research Institute (FBRI) at VTC, the Virginia Tech Corporate Research Center (VTCRC) or a designated site. All staff (including recruitment staff) will have completed human subjects' protection and research training. We have a history of successful recruitment of cigarette smokers and NVP users. All participants will enroll on a voluntary basis and sign an IRB-approved consent form prior to study participation.

6.0 Study Intervention(s)/Investigational Agent(s)

7.1 Describe the study interventions (including behavioral interventions) and/or investigational agents (e.g., drugs or devices) to be used in this study. Consider each of the items listed below:

- *Drug/Device Handling: If the research involves drugs or devices, describe your plans to store, handle, and administer the drugs or devices so that they will be used only on subjects, and only by authorized investigators.*
- *Describe whether any of the following will be used: microwaves, X-rays, DEXA scans, general anesthesia, or sedation*
- *If control of the drugs or devices used in this protocol will be accomplished by following an established, approved organizational SOP (e.g., Research Pharmacy SOP for the Control of Investigational Drugs, etc.), please reference the SOP in this section.*

This study does not involve any smoking cessation interventions. This study does involve experimental manipulation of narratives and of tobacco/nicotine product price to understand consumer's behavior. No drugs or devices will be provided to participants.

6.2 List the name of all drugs (including any vitamins, supplements, herbs, or nicotine) to be used in the study. Indicate whether they have FDA approval, and list any limitations for their use:

The range of products available to sample and purchase includes: cigarettes, chewing tobacco (dip), nicotine gum, nicotine lozenges, e-cigarettes, and snus. All the products that will be available to sample and purchase are FDA approved and available in the real world.

6.3 List all devices, how they will be used, their purpose in the study, and if they will be used in a manner consistent with their approved uses. If they will be used in ways that are not yet FDA approved, indicate whether they

22-432 Effects of narratives on demand for low and high ventilated cigarettes and substitution for alternative products.

need an IDE or a determination that they are exempt from the IDE Determination. If a determination of significant risk or non-significant risk is needed for any of the devices, include the researcher's recommendation for each of those devices:

N/A

6.4 *If the drug is investigational (has an IND) or the device has an IDE or a claim of abbreviated IDE (non-significant risk device), include the following information:*

- *Identify the holder of the IND/IDE/abbreviated IDE.*
- *Explain procedures followed to comply with sponsor requirements for FDA regulated research for the following:*

FDA Regulation	Applicable to:		
	IND Studies	IDE studies	Abbreviated IDE studies
21 CFR 11	X	X	
21 CFR 54	X	X	
21 CFR 210	X		
21 CFR 211	X		
21 CFR 312	X		
21 CFR 812		X	X
21 CFR 820		X	

N/A

7.0 Procedures Involved

7.1 Describe and explain the study design:

In a between-group within-subject repeated measures design, participants will be randomized to one of three groups (narrative, fact sheet, or control) and complete questionnaires on a computer, sample a range of tobacco products, and complete ETM conditions. Specifically, participants will purchase tobacco products in an online store under five ETM conditions, which include six trials each assessing different cigarette prices: a) high-ventilated cigarette alone, b) low-ventilated cigarette alone, c) high- and low-ventilated cigarette with high-ventilated cigarettes increasing in price, d) high- and low-ventilated cigarette with low-ventilated cigarettes increasing in price, and e) usual, high- and low-ventilated cigarette with usual cigarettes increasing in price.

7.2 *Provide a description of:*

- *All research procedures being performed*
- *If the study has more than one procedure, session, and/or subject population, describe each procedure, session, and/or study population separately. For complex studies, you are encouraged to include a figure or chart.*

Participants will complete 1) an informed consent and assessment session, 2) an ETM session, and a 3) follow-up session. Session 1 and 2 will be separated by an at home sampling phase and Session 2 and 3 will be separated by an at home product use phase.

1) In the consent and initial assessment session, participants will go through standard consent procedures and then provide a breath to confirm recent levels of smoking. Participants will complete a timeline follow back to assess previous month recent smoking, and consumption of nicotine products, and to determine ETM budget. A survey will administer demographics questions and nicotine/tobacco-related assessments (Wisconsin Index of Smoking Dependence Motives, Fagerstrom Test of Cigarette Dependence, Minnesota Nicotine Withdrawal Scale, Perceived Health Risk ratings). At the end of the session, participants will experience a trial of the ETM that will be used in the next session.

For the sampling phase, participants will be provided two days worth of study cigarettes based on their number of cigarettes smoked per day, half of high-ventilated cigarettes and half of low-ventilated cigarettes. Participants will also be provided with a sample of other commercially available tobacco product to try. Participants will be instructed the order in which to use the products on the next three days. The order will be counterbalanced across participants.

During the sampling phase, participants will receive text messages asking how many of each product they sampled during those days.

2) Before the ETM session, participants will be randomized to the narrative, the fact sheet or the control group. In the ETM session, they will listen to a recording of a narrative of an individual who quit tobacco products or a fact-sheet with overall rates of smoking and its negative consequences. Participants in the control group will not be exposed to any recording. Then, participants will buy tobacco products to use throughout the next 7 days. Participants will complete a total of 30 purchasing trials each for 7 days' worth of products. They will be exposed to 5 conditions with cigarettes increasing in price. A balanced Latin square design will be used to present the following conditions: a) a) high-ventilated cigarette alone, b) low-ventilated cigarette alone, c) high- and low-ventilated cigarettes with high-ventilated cigarettes increasing in price, d) high- and low-ventilated cigarettes with low-ventilated cigarettes increasing in price, and e) usual, high- and low-ventilated cigarettes with usual cigarettes increasing in price. Additionally, participants will complete the Questionnaire on Smoking Urges-Brief, the Product Evaluation Scale, questions about the cigarette harshness, items of the Transport Narrative Questionnaire (narrative and fact sheet groups only), the Positive and Negative Affect Schedule

22-432 Effects of narratives on demand for low and high ventilated cigarettes and substitution for alternative products.

(narrative and fact sheet groups only), a manipulation check and an open-ended question about the recording they listened (narrative and fact sheet groups only), and the Experiment/Experimenter Attitudes Rating Scale.

For the seven days following the ETM session, participants will be asked not to use or purchase any outside tobacco/nicotine products and not to sell or give away any of their purchases.

3) In the follow-up session, participants will complete a timeline follow back to assess previous week recent smoking, and consumption of nicotine products and questions about their experience with high- and low- ventilated cigarettes. Session 3 will be conducted over the phone.

7.3 *Describe:*

- *Procedures or safeguards intended to reduce the probability and magnitude of risks. (For example: Reducing the risk of injury in a virtual reality study either by having the subjects sit during the study or by providing an obstacle-free space for walking.)*
- *Be sure to describe all drugs and devices used in the research, when they will be administered or used, and their purpose.*
- *Methods used to collect data about subjects. Please upload all data collection forms to Protocol Management. Some common examples are:*
 - *Screening questionnaires*
 - *Survey(s), including online surveys*
 - *Demographic questionnaire(s)*
 - *Interview guide(s), e.g., questions or pool of questions for semi-structured interviews*
 - *Focus group guide(s)*
 - *Other documents used to collect data*

Participation in this study is completely voluntary and participants may choose not to participate at any time.

Information and data from participants will be collected from research staff and from self-reported surveys. Examples of the assessments described in section 8.2 are attached.

7.4 *What data will you collect during the study and how you will obtain them? Please include descriptions of electronic data collection, database matching, and app-based data collection:*

22-432 Effects of narratives on demand for low and high ventilated cigarettes and substitution for alternative products.

All of the survey and questionnaire data will be collected using Qualtrics, an online survey platform used to develop, administer, and collect participant data in a secure password protected database.

ETM data will be collected using an experimental online store custom-built by a programmer and used in previous studies.

All tasks will be performed on a computer. Only study personnel will have access to the collected data.

7.5 Who will transcribe or code audio and/or video recordings?:

N/A

7.6 Include a description of any deception to be used in the study. Include justification for the use of deception (why the deception is necessary), describe the debriefing process, and describe how the study meets all the following criteria for alteration of consent (deception is considered an alteration of informed consent):

- *The research involves no more than minimal risk to the subjects*
- *The alteration will not adversely affect the rights and welfare of the subjects*
- *The research could not practicably be carried out without the alteration/deception*
- *(Optional but encouraged in most cases) Subjects will be provided with additional pertinent information after participation (i.e., debriefing for studies involving deception)*

N/A

7.7 If the study involves long-term follow-up (once all research related procedures are complete), describe what data will be collected during the follow up period and when it will occur:

N/A

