4.0 Study Design and Statistical Analysis Plan

4.1 *Describe the basic study design/approach (e.g., qualitative study using five focus groups of first year students to describe assimilation into the university community; randomized controlled trial of a behavioral change intervention to increase dietary intake of whole grains; pre- post-test evaluation of new pedagogical techniques to improve adult literacy):*

In a between-group within-subject repeated measures design, participants will be randomized to one of three groups (narrative, fact sheet, or control) and complete five ETM conditions, which include six trials assessing different cigarette prices: a) high-ventilated cigarette alone, b) low-ventilated cigarette alone, c) high- and low-ventilated cigarette with high-ventilated cigarettes increasing in price, d) high- and low-ventilated

22-432 Effects of narratives on demand for low and high ventilated cigarettes and substitution for alternative products.

cigarette with low-ventilated cigarettes increasing in price, and e) usual, high- and low-ventilated cigarette with usual cigarettes increasing in price.

4.2 *Describe corresponding data analysis plan/approach (e.g., content analysis of focus group transcripts; descriptive analysis followed by linear regression modeling; nonparametric analysis of pre- and post-test measures):*

A within-between subject analysis of variance (ANOVA) will test for differences in substitution and demand measures between groups (narrative, fact sheet, and control) and condition (e.g., high-ventilated cigarettes alone). We will test for the interaction between group and condition, suggesting a difference in how each group responds to different conditions. Order effects will be included in all models to account for the balanced Latin square design for counterbalancing the ETM conditions within the session. We will perform post-hoc contrasts to compare groups, based on our hypothesis.

Additional analyses might be conducted.

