**NCT: NCT05487625**

**Document date: 09/13/2022**

### ***Study Design and Statistical Analysis plan***

In a between-group within-subject repeated measures design, participants will be randomized to one of three groups (narrative, fact sheet, or control) and complete five ETM conditions, which include six trials assessing different cigarette prices: a) high-ventilated cigarette alone, b) low-ventilated cigarette alone, c) high- and low-ventilated cigarette with high-ventilated cigarettes increasing in price, d) high- and low-ventilated cigarette with low-ventilated cigarettes increasing in price, and e) usual, high- and low-ventilated cigarette with usual cigarettes increasing in price.

A within-between subject analysis of variance (ANOVA) will test for differences in substitution and demand measures between groups (narrative, fact sheet, and control) and condition (e.g., high-ventilated cigarettes alone). We will test for the interaction between group and condition, suggesting a difference in how each group responds to different conditions. Order effects will be included in all models to account for the balanced Latin square design for counterbalancing the ETM conditions within the session. We will perform post-hoc contrasts to compare groups, based on our hypothesis.

Additional analyses might be conducted.

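### The Session 1 marketplace trial, done by everyone before the message, has no fixed content and no stated analysis use, so the group contrasts give up precision that would cost almost nothing to obtain

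*Protocol*

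**What the plan says.** Protocol section 7.2 sets the order of events. Session 1 covers consent, breath sample, a past-month timeline follow back that also sets the ETM budget, and questionnaires. It closes with one exposure to the marketplace: "At the end of the session, participants will experience a trial of the ETM that will be used in the next session". No price, product list, budget or purpose is given for it. Next, "Session 1 and 2 will be separated by an at home sampling phase". Allocation comes later: "Before the ETM session, participants will be randomized to the narrative, the fact sheet or the control group". The recording is played (none for control), and only after that does the scored purchasing begin: "Then, participants will buy tobacco products to use throughout the next 7 days". All of it is post-message: "Participants will complete a total of 30 purchasing trials each for 7 days' worth of products", which is five conditions at six prices each.

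The analysis is stated in the same terms in protocol section 4.2 and the SAP: "A within-between subject analysis of variance (ANOVA) will test for differences in substitution and demand measures between groups (narrative, fact sheet, and control") and between conditions. On the interaction, the SAP says "We will test for the interaction between group and condition, suggesting a difference in how each group responds to different conditions". The only other model term is order: "Order effects will be included in all models to account for the balanced Latin square design for counterbalancing the ETM conditions within the session". Post-hoc group contrasts follow. Neither document names a baseline covariate. The hypothesis in section 2.2 concerns purchases under the narrative compared with the fact sheet.

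**The concern.** Every level of the within-subject factor is an ETM condition measured after the message, so the repeated measures never compare a person before and after it. The primary hypothesis is therefore tested between persons. Stable differences in how much people buy, and how they split a budget between cigarettes and alternatives, stay in the error term of that contrast.

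With 30 per arm, the difference between two arms in any baseline measure has a standard deviation of sqrt(2/30) = 0.26 SD. Chance differences of up to about 0.5 SD (1.96 × 0.26) are therefore ordinary. A pre-message reading in the same store would allow this to be seen and adjusted for. The occasion for such a reading is already in the schedule, but as written it is neither standardised nor assigned to the analysis. What is at stake is the precision of the narrative-versus-fact-sheet contrast and a look at balance on marketplace behaviour.

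**Working it through.** **1. The plan's own figure.** Inputs from protocol section 13.1: three groups, two measurements, f = 0.25, alpha = 0.05/5 = 0.01, power 95%, 90 completers. The within-person correlation is not given; assume 0.5 and sphericity. For the within-between interaction:

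- Noncentrality = f² × N × m/(1 − rho) = 0.0625 × 90 × 2/0.5 = 22.5, with 2 and 87 df.
- Power is 95.7%. The smallest N reaching 95% is 88, or 90 in equal thirds. Attrition: 90/0.9 = 100.

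The stated sample size reproduces. It belongs to an interaction, in which stable differences between persons cancel.

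**2. The same inputs applied to a group difference.** Take the mean of the five post-message conditions. Its variance relative to one reading is (1 + 4 rho)/5, which is 0.6 at rho = 0.5. Noncentrality = 0.0625 × 90/0.6 = 9.375, and power at alpha 0.01 is 55%. Over rho = 0.3, 0.5 and 0.7, power is 73%, 55% and 42%. The between-person comparison is where extra precision is needed.

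**3. What one baseline covariate does.** Let r be the correlation between the Session 1 purchase and the Session 2 outcome (assumed). Residual variance is multiplied by 1 − r² and the standard error by sqrt(1 − r²). The equivalent number of completers is 90/(1 − r²).

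| r | 1 − r² | SE factor | SE reduction | Equivalent completers |
|---|---|---|---|---|
| 0.3 | 0.91 | 0.954 | 5% | 99 |
| 0.5 | 0.75 | 0.866 | 13% | 120 |
| 0.7 | 0.51 | 0.714 | 29% | 176 |

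**4. Power for narrative versus fact sheet.** Two-sided t test, 30 per arm, alpha 0.01. Noncentrality = d × sqrt(15)/sqrt(1 − r²), with 58 df unadjusted and 57 with the covariate. Neither d is in the documents. The value 0.5 is the usual conversion 2f = 2 × 0.25. The value 0.65 rescales it to the mean of five conditions at rho = 0.5: 0.5/sqrt(0.6) = 0.645.

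| Assumed d | No covariate | r = 0.3 | r = 0.5 | r = 0.7 |
|---|---|---|---|---|
| 0.5 | 24% | 27% | 34% | 52% |
| 0.65 | 45% | 50% | 60% | 80% |

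For the three-group F test of step 2 at rho = 0.5, the noncentrality 9.375/(1 − r²) becomes 10.3, 12.5 and 18.4, and power goes from 55% to 60%, 71% and 90%.

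**5. The interaction.** The group-by-condition test uses only differences between conditions within a person. A covariate with one value per person and one common slope shifts all five of that person's conditions equally and drops out of every such difference. It therefore leaves the interaction sum of squares, its error term and its F unchanged. Only a slope that varies by condition can alter that test.

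**The case against.** The strongest reply is that a randomised post-only comparison needs no baseline. That stands. A reader might infer that pre-message group differences are confounded with the message effect. The documents do not support this: allocation follows Session 1, so such differences arise by chance, are already reflected in the standard error, and do not bias the contrast.

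A reader might also infer that the Session 1 trial serves only as familiarisation, that its purchases are discarded, or that it already runs on the participant's own budget. Section 7.2 says none of these. It states no purpose, and it links the budget to the timeline follow back without saying that the Session 1 trial uses it. Section 7.4 says the online store collects ETM data and excludes no session. What can be said is that no analysis use is stated.

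Three further objections limit the size of the gain, and all stand:

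- r may be low. The trial precedes sampling of the study cigarettes, and usual cigarettes are named in only one of the five conditions.
- The endpoint in section 3.4 is substitutability as a function of price. A single trial can give a purchase level, but not a baseline demand curve or cross-price slope.
- Past-month use and the dependence scales are already collected before the message. The figures above compare a covariate with none, so part of the gain might come from those measures instead. They are not named in the model either, and the sentence allowing additional analyses prespecifies nothing.

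**Conclusion.** The point holds as one of efficiency. The planned comparison is valid, but the plan leaves a pre-message use of the outcome instrument without fixed content or a role in the analysis, while its primary hypothesis rests on a between-person contrast with about 30 per arm. The standard error could fall by 5% to 29% for r between 0.3 and 0.7. The corresponding power gain for the pairwise contrast runs from 3 percentage points (d = 0.5, r = 0.3) to 35 (d = 0.65, r = 0.7). These sizes rest on assumed r, d and rho, and the reasons to expect a modest r point to the lower part of the range. The benefit applies to the group main effect and the group contrasts. It does not reach the group-by-condition interaction unless the covariate's slope may differ by condition.

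**What to change.** In protocol section 7.2, define the Session 1 ETM trial as one standard screen for everyone: usual cigarettes and all alternative products at fixed prices, with the participant's own budget. State that the purchases are saved.

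In protocol section 4.2 and the SAP, prespecify the Session 1 purchase of the matching product class (cigarettes for cigarette outcomes, alternatives for alternative-product outcomes) as a covariate for the group main effect and the post-hoc group contrasts. If it is also meant to sharpen the group-by-condition test, add a covariate-by-condition term. Say whether past-month use from the timeline follow back enters as well.

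The cost is small: no added visit or task, since the trial is already run; one fixed screen and a saved record; 1 df for the covariate and 4 more for the covariate-by-condition term (five conditions minus one). The main risk is that r turns out low and little is gained.
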